Participants who meet any of the following criteria at screening or prior to dosing of SPK-8016 (Day 0) are not eligible for the study:

1. Have active hepatitis B or C. All participants must be screened for both active hepatitis B and C regardless of prior known history.
 - a. **Screening for hepatitis B:** All participants must have a single sample collected at screening for each of the following tests: HBsAg (hepatitis B surface antigen), anti-HBc (total Hepatitis B core antibody), and Hepatitis B virus (HBV)-DNA viral assay (nucleic acid test for hepatitis B virus DNA).
 - i. A participant is not eligible if either HBsAg is positive or HBV-DNA is positive/detectable.

- ii. A participant is eligible if the anti-HBc is positive and both HBsAg and HBV-DNA are negative, as this would be consistent with a prior infection of hepatitis B. Anti-HBc must be obtained in all participants to discriminate between acute infection and possible reactivation of hepatitis B during the trial (e.g., in participants with no prior history of hepatitis B).
- b. **Screening for hepatitis C:** All participants, including those who have never been treated or who have completed anti-viral therapy for chronic hepatitis C, must have a single Hepatitis C virus (HCV)-ribonucleic acid (RNA) load assay (also referred to as a nucleic acid test [NAT] for HCV RNA) at screening.
 - i. A participant is not eligible if his HCV-RNA load assay is positive/detectable.
 - ii. A participant treated with anti-viral therapy for chronic hepatitis C must have completed anti-viral therapy at least 6 months prior to screening and must have a negative HCV-RNA at the time of screening.
 - iii. A participant with a documented or self-reported history of HCV must have a single negative HCV-RNA at the time of screening.
- 2. Are currently on antiviral therapy to treat their hepatitis B or C
- 3. Have significant underlying liver disease. A participant is not eligible with any of the following documented diagnoses, indicative of significant underlying liver disease:
 - a. Portal hypertension; *or*
 - b. Splenomegaly; *or*
 - c. Hepatic encephalopathy.

Any participant without any of these pre-existing diagnoses must have the following performed at screening:

- a. Serum albumin measurement. A participant is not eligible if the serum albumin level is below the lower limit of normal of the laboratory; *and*

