19. Quality-of-life questionnaires (Hemophilia Activities List, Haem-A-QoL, EQ-5D-5L) will be completed by the participants.
20. Training and dispensation of FVIII Infusion Log at Day 0, collect, review, and dispense at subsequent visits.
21. Spare plasma will be collected for further coagulation assays, future research, or for clarification of any clinical or laboratory AEs.
22. Unscheduled visits or safety tests may be performed for safety monitoring purposes or repeat safety assessments.
23. If the long-term follow-up (LTFU) study is not enrolling at the time of a participant's planned Week 52 visit, the participant may remain in SPK-8016-101. The procedures from Week 46, except for collection of immunology samples for ELISpot, will be performed at Week 52 every 12 weeks until the LTFU study is open. At that time, the week 52/EOS visit should occur. The Week 52 procedures are to be performed only at the EOS Visit.
24. Any concomitant medication that has known hepatotoxicity should be discontinued in the first 12 weeks following vector infusion.
25. Local hematology, local liver function, and central immunology and immune profiling must be obtained 3 to 7 days prior to Day 0. A remote service provider may be used for this visit. Contact the participant to verify no changes in the general health status prior to first dose of [REDACTED].
26. Hematology should be monitored weekly and lipid profile monthly for Cohort 1 and 2 until [REDACTED] dosing has stopped. The frequency may be altered based on clinical response.
27. In Cohort 2, [REDACTED] following Day 0 and may be considered based on clinical/immune response in consultation with the Sponsor. See Section 4.1.1
28. In Cohort 1, [REDACTED]
29. Participants in cohort 1 and 2 will be retested at Day 84 for HBsAg and anti-HBc.
30. Immune profiling will be collected prior to the immunomodulation [REDACTED] 3-7 days prior to Day 0, pre-administration of SPK-8016, and 30 (\pm 2) minutes, 2 hr (\pm 10 min), 5 hr (\pm 10 min), and 24 (\pm 1) hours post vector infusion, and Days 7, 14, 21, 28, 56, and Week 16.
31. PAX gene will be collected prior to the immunomodulation [REDACTED], pre- administration of SPK-8016, 5 hr (\pm 10 min) and 24 (\pm 1) hours post vector infusion, and Days 14, 28, and 56.

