32. If an apparent CTL immune response/liver inflammation is observed and triggers the initiation of reactive corticosteroids, please collect additional samples for "Immune Profiling" and "PAX gene" at the following times: prior to initiating [REDACTED] corticosteroids or oral corticosteroids (if possible, without delaying the initiation of corticosteroid therapy) and then week 1 (\pm 2 days) and Week 2 (\pm 2 days) following initiation of corticosteroids.
33. Anti-SARS-CoV2 serology testing at baseline and at week 18. At the discretion of the Investigator, Nucleic acid amplification testing (NAAT) for infection with SARS-CoV2 may be performed 3 to 7 days prior to Day 0 (Cohort 2 only) and prior to the initiation of reactive corticosteroids.
34. If the PK Profile is not available in historical records on the current FVIII product, the participant must undergo a PK analysis locally at Screening or Day 0.
35. Fibrinogen antigen, Thrombin Time (TT), D-dimer are required at Screening, Day 10 and Day 24 for participants enrolled in Cohort 2.

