2.2.5 Summary of Non-Clinical and Clinical Experience with [REDACTED]

Pre-clinical studies of hepatic artery administration of AAV8-hAAT-hFIX16 were performed in rhesus macaques; in these studies, vector was given alone or together with a short course of

immunomodulation to assess the potential safety and efficacy of the approach. [REDACTED]

[REDACTED]
The [REDACTED]
[REDACTED] and contained the wild type copy of the hFIX cDNA.

[REDACTED]
[REDACTED]
[REDACTED]
[REDACTED]

The regimen of [REDACTED]
[REDACTED]

[REDACTED] The side effect profile was acceptable and there were no SAEs on this regimen. The side effects of immunomodulatory drugs are well described (Post, 2005; Perry, 2005) and include the risk of hepatitis virus reactivation (Savas, 2007; Melon, 2005; Lalazar, 2007; Francisci, 2006; Calabrese, 2006) and the occurrence of B cell lymphoproliferative disorders (Gross, 1999; Pascual, 2007; Bakker, 2007). [REDACTED]

[REDACTED]
[REDACTED]

[REDACTED]
[REDACTED]
[REDACTED]
[REDACTED]
[REDACTED]
[REDACTED]
[REDACTED]

[REDACTED]
[REDACTED]

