5.2 Exclusion Criteria

Participants who meet any of the following criteria at screening or prior to dosing of SPK-8016 (Day 0) are not eligible for the study:

1. Have active hepatitis B or C. All participants must be screened for both active hepatitis B and C regardless of prior known history.
 - a. **Screening for hepatitis B:** All participants must have a single sample collected at screening for each of the following tests: HBsAg (hepatitis B surface antigen), anti-HBc (total Hepatitis B core antibody), and HBV-DNA viral assay (nucleic acid test for hepatitis B virus DNA).
 - i. A participant is not eligible if either HBsAg is positive or HBV-DNA is positive/detectable.
 - ii. A participant is eligible if the anti-HBc is positive and both HBsAg and HBV-DNA are negative, as this would be consistent with a prior infection of hepatitis B. Anti-HBc must be obtained in all participants to discriminate between acute infection and possible reactivation of hepatitis B during the trial (e.g., in participants with no prior history of hepatitis B).
 - b. **Screening for hepatitis C:** All participants, including those who have never been treated or who have completed anti-viral therapy for chronic hepatitis C, must have a single **HCV-RNA load assay (also referred to as a nucleic acid test [NAT] for HCV RNA)** at screening.
 - i. A participant is not eligible if his HCV-RNA load assay is positive/detectable.
 - ii. A participant treated with anti-viral therapy for chronic hepatitis C must have completed anti-viral therapy at least 6 months prior to screening and must have a negative HCV-RNA at the time of screening.
 - iii. A participant with a documented or self-reported history of HCV must have a single negative HCV-RNA at the time of screening.
2. Are currently on antiviral therapy to treat their hepatitis B or C
3. Have significant underlying liver disease. A participant is not eligible with any of the following documented diagnoses, indicative of significant underlying liver disease:
 - Portal hypertension; *or*
 - Splenomegaly; *or*
 - Hepatic encephalopathy.

Any participant without any of these pre-existing diagnoses must have the following performed at screening:

- a. Serum albumin measurement. A participant is not eligible if the serum albumin level is below the lower limit of normal of the laboratory; **and**

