Liver Function Tests and CRP (CL and LL)	
 
  
 • Albumin, • Total bilirubin • Direct bilirubin • Indirect bilirubin 	 
 • ALP • AST • ALT 	 
 • Total protein • GGT • LDH • CRP 	
 
	
 • Albumin, • Total bilirubin • Direct bilirubin • Indirect bilirubin 	
 • ALP • AST • ALT 	
 • Total protein • GGT • LDH • CRP 	

 • Albumin, • Total bilirubin • Direct bilirubin • Indirect bilirubin 	
 • ALP • AST • ALT 	
 • Total protein • GGT • LDH • CRP 			
Coagulation (CL, LL as noted)	
 • FVIII activity, aPTT (CL and LL) • FVIII antigen (CL) • FVIII inhibitor (Nijmegen Bethesda) (CL, LL at screening), VWF antigen, VWF activity (CL) • Spare Plasma 				
Neutralizing Antibody (CL)	██████████ Neutralizing Antibody				
Immunology (CL)	
 • Immun PBMC for ELISpot • Immun PBMC for Inflamm 				
Immune Profiling (CL)	
 • Cytokine/Chemokine Analysis • Tryptophan metabolites • Complement activation 				
PAX Gene (CL)	
 • PAX Gene (RNA) 				
Vector Shedding (CL)	
 
  
 • Urine • Serum 	 
 • Saliva • Semen 	
 
	
 • Urine • Serum 	
 • Saliva • Semen 		

 • Urine • Serum 	
 • Saliva • Semen 				

Assessment	Description
HBV, HCV (CL)	
 • Hepatitis B surface antigen • Hepatitis B core antibody total • Hepatitis B core antibody total • HCV RNA Ampliprep Taqman 2.0 • HBV DNA Ampliprep Taqman 2.0DIL • HBV DNA Ampliprep Taqman 2.0
HIV Serology (CL)	HIV-1/HIV-2 Antibody Screen HIV-1/HIV-2 Antigen Screen
Viral load and CD4 (CL)	HIV-1/HIV-2 Viral Load, CD4+ Count
TPMT (LL)	TPMT activity or genotype
Lipid Profile (LL)	Lipid profile (Cholesterol LDL, VLDL, and HDL, triglycerides)
TB (LL)	Tuberculosis Interferon-gamma Release Assay
SARS-CoV-2 Testing (LL)	anti-SARS-CoV-2 serology NAAT for infection with SARS-CoV-2

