6.8 Follow-up Observation Period (Weeks 1-52)

Visits during the follow-up period may occur at either the vector-administration or follow-up center. Any visit requiring a physical exam must be performed at the study center. All other visits without a physical exam may be performed by a qualified and trained in-home service provider.

U.S. Centers for Disease Control and Prevention (CDC) guidance on hygiene, travel, and social interactions will be considered by the Investigator and Sponsor to minimize the risk of community acquired viral infections. This may include recommending a shelter in place and/or other social distancing measures during immunomodulation. *FDA Guidance for Industry, Investigators, and Institutional Review Boards on Conduct of Clinical Trials of Medical Products during COVID-19 Pandemic (2020)* will provide considerations to assist in assuring the safety of trial participants. International and local health guidelines may be observed for sites outside of the United States.

6.8.1 Days 3, 7, 10, 14, 17, 21, 24, 28, 31, 35, 38, 42, 45, 49, 52, 56, 59, 63, 66, 70, 73, 77, 84 (± 2 days)

A minimum of twice weekly visits is required from Weeks 1-11 to monitor for a potential rise in hepatic transaminases and/or loss of FVIII transgene expression. Visits at Weeks 1-11 may be performed by an in-home service provider.

If an apparent immune response/liver inflammation is observed and triggers the initiation of reactive corticosteroids, additional samples are to be collected for Immune Profiling and PAX Gene prior to corticosteroid administration, if possible, and then Week 1 (± 2 days) and Week 2 (± 2 days) following initiation of corticosteroids (see Table 1 and Section 4.1.3.1).

If immunomodulation is initiated, weekly visits should continue to collect transaminases, FVIII (local and central lab), Immunology. Weekly hematology and monthly lipid profile results should also be monitored locally for Cohorts 1 and 2 until [REDACTED] dosing has stopped, and this may be altered based on clinical response. Social distancing may be recommended for the duration of immunomodulation.

The following procedures will be performed at all visits unless otherwise noted:

- Perform physical examination, including weight (*Days 3, 49, 84*)
- Measure vital signs (*Days 3, 49, 84*)
- Hemophilia Activities List, Health Economic Assessment (*Days 49 and 84*)
- Review FVIII Infusion Log (*Days 49, 84*)

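### For men anti-HBc positive at screening, the Day 84 hepatitis B retest in Cohorts 1 and 2 leaves out HBV-DNA, one of the two markers the protocol uses to define active infection

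*Protocol*

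**What the plan says.** **Entry.** Exclusion criterion 1a (synopsis and Section 5.2) requires HBsAg, anti-HBc and HBV-DNA in every candidate. The rule is: "A participant is not eligible if either HBsAg is positive or HBV-DNA is positive/detectable". Past infection does not exclude: "A participant is eligible if the anti-HBc is positive and both HBsAg and HBV-DNA are negative". Section 5.2 explains that anti-HBc is taken so that acute infection can be told apart from "possible reactivation of hepatitis B during the trial".

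**On study.** Footnote 29 gives the only hepatitis B retest in the readable text: "Participants in cohort 1 and 2 will be retested at Day 84 for HBsAg and anti-HBc". Table 3 (Section 6.3) lists "HBV DNA Ampliprep Taqman 2.0" among the central laboratory assays but attaches no visit to it. Sections 6.8.1 and 6.8.2 name no hepatitis B test at any follow-up visit.

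**Risk.** Section 2.2.5 says that the side effects of immunomodulatory drugs "include the risk of hepatitis virus reactivation".

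**At a steroid trigger.** Section 6.8.1 says that "additional samples are to be collected for Immune Profiling and PAX Gene prior to corticosteroid administration", and footnote 32 matches it. Section 4.1.3.1 adds nucleic acid testing for SARS-CoV-2 at this point. The readable text names no hepatitis B test there, but Section 4.1.3.1 is redacted just after its opening clause.

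**The concern.** The protocol sets a two-marker standard for active hepatitis B at entry and then checks only one of the two on study. The gap falls on the men for whom reactivation is the question, namely those with evidence of past infection who are given immunomodulation. A man in this group with negative HBsAg and detectable HBV-DNA would have been refused entry. At Day 84 the same man would show nothing new on the specified panel.

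The main stake is participant safety: direct detection of reactivation while immunomodulation is in use.

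A second stake arises only when transaminases rise. Three items depend on whether a liver event is attributed to the vector:

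- the suspension rule in Section 4.3 for vector-related elevations that do not resolve within 4 weeks on immunomodulation;
- the matching adverse event of special interest in Section 9.1.3;
- the split of adverse events into vector-related and immunomodulation-related in SAP Sections 1.2.3 and 3.4.2.

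The primary safety endpoint on transaminase elevation requiring immunosuppression (Section 3.3) carries no relatedness condition and is not affected.

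**Working it through.** The plan gives no figure to reproduce here. The check is a comparison of test panels, with some simple counting.

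**1. The panels side by side** (Section 5.2, criterion 1a; Table 1, footnote 29)

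| Test | At screening | Excludes if positive | Day 84 retest |
|---|---|---|---|
| HBsAg | yes | yes | yes |
| anti-HBc | yes | no | yes |
| HBV-DNA | yes | yes | not listed |

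Tests repeated: 2 of 3. Disqualifying markers repeated: 1 of 2.

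**2. What each Day 84 result can show in a man already anti-HBc positive**

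- Anti-HBc positive again: compatible with the state in which he was admitted, so it says little.
- HBsAg newly positive: meets the protocol's own definition of active infection, and is detected.
- HBsAg negative with HBV-DNA detectable: also meets that definition, but is not looked for.

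For a man who was anti-HBc negative at entry, a new positive anti-HBc is itself informative. The gap therefore matters most in the anti-HBc-positive subset.

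**3. Timing against immunomodulation.** The Cohort 1 regimen runs for 13 weeks after infusion (synopsis, Sequence of Enrollment): 13 × 7 = Day 91. Day 84 is 91 − 84 = 7 days before it ends, so the retest is made on treatment. This calculation applies to Cohort 1 only.

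**4. Timing against transaminase events.** In the four men already treated, reactive steroids began about 3 to 6 weeks after infusion (synopsis, Rationale): 3 × 7 = Day 21 to 6 × 7 = Day 42. Day 84 is 84 − 42 = 42 to 84 − 21 = 63 days later. Those men did not receive the Cohort 1 or Cohort 2 regimens, so timing may differ in the new cohorts. On this evidence, though, a fixed Day 84 sample comes too late to help explain such events.

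**5. Size of the subset.** The plan is to dose up to 40 men, of whom 4 were dosed before Cohorts 1 and 2. At most 40 − 4 = 36 could enter these cohorts under the planned maximum. The documents do not say how many would be anti-HBc positive, so the range is 0 to 36.

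**The case against.** The strongest objection is that the controlling schedule cannot be seen. Section 6 sends the reader to Table 1 for all safety timepoints, and the Table 1 grid and the footnotes before 13 are missing from the public copy. The agent-specific parts of Section 2.3.1.7 are largely redacted. A reader might infer that the study has no HBV-DNA monitoring at all. The documents do not support that, because a test may be scheduled in text that is not visible. What stands is narrower: footnote 29 is complete and unredacted, and it does not name HBV-DNA.

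Second, the men are watched closely in other ways. Visits are at least twice weekly in Weeks 1 to 11, liver function tests are done locally and centrally at each visit, and weekly transaminase checks continue if immunomodulation is initiated. Unscheduled safety tests are allowed (footnote 22), spare plasma is archived (Section 6.2.6) and is listed for Day 84, experts can be consulted (Section 4.1.3.4), and alternative causes are to be considered (Section 9.3.2). This is real mitigation. But the liver tests are not specific to hepatitis B, and none of the other provisions calls for HBV-DNA.

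Third, an entry rule and an on-study check need not use the same panel, and footnote 29 sets no pass or fail rule. That is correct, so the mismatch is a design choice open to improvement and not a contradiction. Nor do the documents give data on whether HBV-DNA turns positive before HBsAg. A claim of earlier detection would go beyond them.

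Two other inferences should be resisted. One is that a Day 84 HBV-DNA test would sort out the cause of earlier transaminase rises; step 4 of the working shows why it would do little. The other is that the retest will be missed because Section 6.8.1 does not list it. Since Table 1 governs timepoints and footnote 29 states the retest, that omission is editorial.

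**Conclusion.** The point holds as a cheap improvement. For men anti-HBc positive at screening, the stated Day 84 retest leaves HBsAg as the only informative hepatitis B marker and omits the other marker of active infection, under drugs the protocol associates with reactivation. Its size is 1 of 2 disqualifying markers unchecked at one visit, in a subset of unknown and possibly zero size.

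The gain from HBV-DNA at Day 84 is direct detection of reactivation, on top of frequent but non-specific liver tests. Help with attribution comes only from a test at the time of a transaminase rise. That part is conditional, because Section 4.1.3.1 is partly redacted.

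The conclusion assumes that the unseen Table 1 content does not already schedule HBV-DNA at Day 84. If it does, the Day 84 part falls away. If redacted text requires hepatitis B testing at a steroid trigger, that part falls away too.

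**What to change.** 1. In footnote 29, add HBV-DNA to the Day 84 retest for participants who were anti-HBc positive at screening, unless the Table 1 grid already schedules it. Leave HBsAg and anti-HBc as they are for everyone in Cohorts 1 and 2.
2. Unless Section 4.1.3.1 already requires it, amend footnote 32 and Section 6.8.1 so that HBsAg and HBV-DNA are drawn in the same subset when a transaminase rise triggers reactive corticosteroids, with treatment not to wait for the result. The protocol already specifies a viral nucleic acid test at this point for SARS-CoV-2, so the step fits existing practice.
3. As an editorial matter only, list the Day 84 retest in Section 6.8.1.

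Cost: one extra assay per affected man at a visit that already draws blood, and one further sample for both markers if a transaminase rise triggers steroids. Both assays are already in the central laboratory list in Table 3. The rest is text edits, and if no man is anti-HBc positive there is no added testing.

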2 INTRODUCTION

2.1 Background

SPK-8016 is an investigational gene therapy medicinal product that contains [REDACTED]

[figure not shown]
SPK-8016 is being developed by Spark Therapeutics for the treatment of hemophilia A.

This clinical study (SPK-8016-101) will evaluate the safety, efficacy, and tolerability of SPK-8016 in adult males with clinically severe hemophilia A and no measurable inhibitor against FVIII. Data obtained from this study will inform the design and dose selection for subsequent studies of SPK-8016 in other patient populations (e.g., those with inhibitors).

2.1.1 Hemophilia A

Hemophilia A is an X-chromosome linked bleeding disorder that primarily affects 1 in 5,000 male births ([Giangrande, 2005](#); [Srivastava, 2013](#)). The severity of disease is characterized by the endogenous level of FVIII measured in the plasma. Severe hemophilia A is defined as a coagulation activity of FVIII in plasma (FVIII:C) of <1% (<1 IU/dL) of normal levels. Factor VIII, a single chain glycoprotein pro-cofactor, is composed of 6 putative domains arranged in the order of a heavy chain (A1, A2, and B regions) and a light chain (A3, C1, and C2 regions). The light chain ([Lollar, 1988](#)) contains binding sites for von Willebrand factor (VWF), activated protein C ([Walker, 1990](#)), activated factor IX (FIXa), and phospholipid ([Foster, 1990](#)). FVIII and VWF circulate in plasma as a non-covalently-linked complex that stabilizes the intrinsically unstable FVIII protein. Observations that the FVIII-VWF complex is dissociated by phospholipids and that VWF prevents FVIII from binding to phospholipids and platelets suggest antagonism between phospholipids and VWF for binding to FVIII. Although VWF and FVIII are glycoproteins, they have different roles in the initiation and regulation of hemostasis. VWF is necessary for mediating platelet-vessel interactions at the site of vascular injury. Thrombin and FIXa each activate FVIII functions by cleaving the light chain at amino acid residue 1689. This cleavage releases FVIII from VWF and allows binding of FVIII to phospholipid resulting in the formation of the tenase-activated factor X (FXa) complex. This is the central step of the coagulation cascade. The coagulation cascade has 2 pathways: the Activation Pathway (Intrinsic Pathway) and the Tissue Factor Pathway (Extrinsic Pathway) ([Makaryus, 2013](#)). The plasma factors normally circulate in inactive forms and are activated in a cascade or “waterfall” of amplifying reactions ([Macfarlane, 1964](#); [Davie, 1964](#)) one after the other until the soluble plasma protein, fibrinogen, is transformed into a fibrinous clot. The blood coagulation cascade is illustrated in Figure 2.

Figure 2: The Blood Coagulation Cascade

Although platelets are critical to the formation of the hemostatic plug, an effective clot cannot be formed without adequate levels of pro-coagulant factors. In normal individuals, the level of coagulation factors in the plasma ranges from 50 - 150% (or 50 -150 IU/dL) of the level in normal pooled plasma. Therefore, in hemophilia, clinical features and factor coagulant activity define the severity of the disease.

